### **8.1.2.6 Reporting of Serious Adverse Events**

Adverse events classified as serious require expeditious handling and reporting to Sponsor or its designee to comply with regulatory requirements.

For any serious adverse event (SAE) that occurs while a patient is on-study; within 30 days of the last study drug administration, regardless of any opinion as to the relationship of the SAE to the study drug; or if any SAE that the Investigator feels is related to the study drug occurs later than 30 days after the last study drug administration, the Sponsor or its designee must be notified immediately (within 24 hours of becoming aware of the event).

### **8.1.2.7 Safety Data Review**

#### ***8.1.2.7.1 Safety Review Committee***

A Safety Review Committee (SRC) comprised of at least three members – one Investigator, a representative from Pelican Therapeutics and the Medical Monitor will evaluate the data obtained at each dose level including a review of all adverse events (serious and non-serious adverse events) as they are reported by the study site. The SRC will recommend whether the dose should be escalated as per protocol, revised to a lower level or intermediate level, halted altogether or more patients are required at the same dose level to evaluate safety.

Ad-hoc SRC meetings may be called for by both the SRC and Sponsor any time during the study if DLTs are observed and/or new safety data warrants immediate action to the conduct of the trial (including events defined by the Study Stopping Criteria in Section [5.5](#)).

The conclusion of the SRC meeting will be documented in meeting minutes. The outcome of the SRC meeting will be communicated to all Investigators.

## **8.2 Efficacy Assessments**

Patient's disease status will be monitored by clinical and radiological assessment (CT scans or MRI) as per RECIST 1.1 criteria where applicable. Patient response per RECIST 1.1 will be evaluated as complete response, partial response, stable disease, or progressive disease.

For the purpose of this study, patients will be evaluated after every 8 weeks  $\pm$  1-week from C1D1, regardless of any delays in treatment cycles. In the event objective response (PR or CR) is noted, changes in tumor measurements must be confirmed by repeat assessments that should be performed at least 4 weeks after the criteria for response are first met. For stable disease (SD), follow-up measurements must meet the SD criteria at least 6 weeks after study entry.

### **8.2.1 RECIST 1.1 Criteria**

Response and progression will be evaluated in this study using the international criteria (version 1.1) proposed by the Response Evaluation Criteria in Solid Tumors (RECIST) Committee (see [APPENDIX II](#)).

Immune response may be a delayed effect, and in immuno-oncology, treatment beyond first progression is commonly used in situations where clinical progression is asymptomatic and/or is not likely to result in life-threatening complications with further progression. Therefore, at the discretion of the Investigator the treatment with PTX-35 may continue despite evidence of radiologic disease progression, and in the absence of clinical deterioration, if the investigator considers this of a potential clinical benefit for the patient, and if the following terms are met: i) no decline in performance status, ii) absence of rapid disease progression or threat to vital organs or critical anatomical sites (e.g., CNS metastasis, respiratory failure due to tumor compression, spinal cord compression) requiring urgent alternative medical intervention, and iii) no significant, unacceptable or irreversible toxicities related to study treatment.

## **8.3 Pharmacokinetics**

Plasma concentrations of PTX-35 will be measured by ELISA at the following timepoints: pre-dose; 30min ( $\pm$ 5min), 2hr ( $\pm$ 5min), 4hr ( $\pm$ 5min), 24hr ( $\pm$ 2hr), 72hr ( $\pm$ 2hr), 144hr ( $\pm$ 2hr), and 216hr ( $\pm$ 2hr) after end of PTX-35 infusion for Cycles 1 and 2, and pre-dose at Cycle 3 only. An approximate 1 mL sample will be collected for each timepoint.

#### **8.4 Analysis of Immunological Effect**

Immune-phenotyping of patient's peripheral blood sample will be performed by flow cytometry, which may include but is not limited to surface and intracellular markers that define naïve T cells (CD4 and CD8), central memory T cells (CD4 and CD8), effector T cells (CD4 and CD8), memory T cells (CD4 and CD8), senescent T cells (cytotoxic and helper), terminal differentiated senescent T cells (cytotoxic and helper), natural killer (NK) cells, natural killer T cells (NKT), T regulatory cells, proliferative T regulatory cells, activated T cells (helper and cytotoxic), proliferative T cells (helper and cytotoxic), T cell markers of exhaustion (helper and cytotoxic; CTLA-4, PD-1, TIGIT, TIM3).

Immune phenotype profiling to determine proportions of NK and T cell subsets for levels of antigen activation, memory and exhaustion will be performed from blood samples (approximately 23 mL) collected on Day 1 (prior to PTX-35 administration) and Day 7 for Cycle 1 and Cycle 2, and at the 30-Day Safety Follow-Up visit.

#### **8.5 Analysis of Immunogenicity**

Approximately 2 mL of blood samples will be drawn for central analysis of anti-therapeutic antibodies (ATA), at the following time-points:

- All Cycles (pre-dose)
- 30-Day Safety Follow-Up Visit

Samples testing positive in the screening assay will undergo a confirmatory assay to demonstrate that the ATAs are specific for the therapeutic protein product. Samples identified as positive in the confirmatory assay will be further characterized in titration and neutralization assays.

#### **8.6 Analysis of response to TENIVAC immunization**

Blood samples collected for immunogenicity will also be used for central analysis of tetanus antibodies, at the following time-points:

- All Cycles (pre-dose)
- 30-Day Safety Follow-Up Visit

#### **8.7 Cytokine Analysis**

Approximately 2 mL of blood samples will be collected at the following time-points during Day 1 of Cycle 1 and Cycle 2 for determination of serum cytokines (e.g., IL-2, IL-4, IL-6, IL-8, IL-10, IL-12, IL-17, IL-22, TNF- $\alpha$ , TGF- $\beta$ , IFN- $\gamma$  and TL1A).

- Day 1: Pre-dose
- Day 1: 2hr  $\pm$  5 minutes from end of PTX-35 infusion

For Cycle 3 and beyond cytokine testing will only be performed if the patient is symptomatic at the time of visit (i.e., flu-like symptoms, fever, or allergic reactions).

## 9.0 STATISTICS

Demographic data and disease-related characteristics will be summarized using descriptive statistics. Categorical variables will be summarized with incidence and percent. Continuous variables will be summarized with n, mean, median, standard deviation and range (minimum and maximum) as appropriate. Data will be presented by each dose cohort. All patient data will be presented in data listings.

### 9.1 Analysis Populations

Safety Evaluable Population: All patients who received at least 1 dose of PTX-35.

DLT Evaluable Population: All patients who receive at least 1 dose of PTX-35 and experience a DLT and/or complete the DLT evaluation period.

Efficacy Evaluable Population: All patients with pre-treatment measurable disease by RECIST 1.1, who received at least 1 dose of PTX-35 and who had at least one radiological assessment during treatment.

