**Statistical Methods and Justification of Sample Size:**

All analyses will be descriptive. Categorical variables will be presented with numbers and, if meaningful, percentages. Continuous variables will be presented by  $n$ , mean, median, standard deviation and range (minimum and maximum) as appropriate. Presentations will be by each dose level.

Safety Evaluable Population: All patients who received at least 1 dose of PTX-35.

DLT Evaluable Population: All patients who receive at least 1 dose of PTX-35 and experience a DLT and/or complete the DLT evaluation period.

Efficacy Evaluable Population: All patients with pre-treatment measurable disease by RECIST 1.1, who received at least 1 dose of PTX-35 and who had at least one radiological assessment during treatment.

This is an exploratory, first-in-human trial. We believe that the sample sizes will be sufficient to characterize the initial safety of PTX-35. No formal sample size calculations have been performed.

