## 5.0 SELECTION AND WITHDRAWAL OF PATIENTS

### 5.1 Inclusion Criteria

Patients **must** meet all of the following inclusion criteria before they will be allowed to participate in the trial:

1. Be willing and have the capacity to sign the written informed consent form.
2. Be male or female of at least 18 years of age at the time of signing informed consent.
3. Have a documented diagnosis of metastatic or advanced, unresectable solid tumor disease. Patient must have progressed or recurred following standard of care (SOC) therapies, or are ineligible for, or who refuse, other safe and effective SOC therapies, and whom the Investigator believes may benefit from experimental treatment with PTX-35.

4. Have an acceptable organ function, as defined below:
  - a. Albumin  $\geq$  2.5 g/dL
  - b. Total bilirubin  $< 3.0 \times$  upper limit of normal (ULN) unless patient has Gilbert's syndrome.
  - c. Alanine transaminase (ALT) and aspartate transaminase (AST)  $\leq 3.0 \times$  ULN, or  $\leq 5 \times$  ULN in the case of liver metastases.
  - d. Calculated or measured creatinine clearance  $> 35$  mL/minute per the Cockcroft-Gault formula.
  - e. Absolute neutrophil count  $\geq 1,500/\text{mm}^3$
  - f. Hemoglobin  $\geq 9$  g/dL.
  - g. Platelet count  $\geq 100,000/\text{mm}^3$
5. Have an Eastern Cooperative Oncology Group (ECOG) performance status of 0 to 2 ([APPENDIX I](#)).
6. Have life expectancy of at least three months.
7. Patients, both females and males, of childbearing/reproductive potential must agree to use adequate contraception, or continuous abstinence, while included in the trial and for six months after the last treatment with PTX-35.

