### **5.4 Withdrawal Criteria**

Protocol therapy will be discontinued at any time if any of the following situations occur:

1. Progressive disease (not including unconfirmed radiographic PD if Investigator opts to continue treatment as outlined in section [8.2.1](#)).
2. Adverse event.
  - The development of toxicity which, in the Investigator's judgment, precludes further therapy.
  - Unacceptable adverse event(s).
  - Intercurrent illness that prevents further administration of treatment.
3. Withdrawal by subject.
4. Lost to follow-up.
5. Non-compliance.
6. At the discretion of the Investigator/physician decision.

7. Death.
8. Pregnancy.
9. Study termination.

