#### **5.4.2 Replacement of Subjects**

Patients who discontinue due to toxicity (related to PTX-35) during the 4-week DLT window of observation of Cycle 1 and Cycle 2, or who do not receive all doses due to toxicity in Cycle 1 and Cycle 2, will not be replaced. Patients who discontinue or who do not receive at least two doses of PTX-35 for any reason other than toxicity during Cycle 1 and 2 will be replaced. Note, that all patients who receive PTX-35 will be included in assessment of DLT per Section [6.1.3](#).

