A post-treatment safety visit will be conducted approximately 30 days following the last dose of PTX-35. Response to treatment will be assessed according to RECIST 1.1 with planned evaluation performed every 8 weeks ( $\pm 1$  week) from the start of treatment (C1D1).

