#### **7.5 Post-Treatment Follow-Up**

Any patient that stops treatment (or starts new anti-cancer treatment) for any reason other than progressive disease will enter the Post-Treatment Follow-Up period, which refers to the time between last dose of PTX-35 and disease progression. The following assessments will be performed every 8 weeks from the date of last scan ( $\pm 1$  week) during the Post-Treatment Follow-Up period:

- Imaging for RECIST 1.1 tumor measurements via CT scan or MRI every 8 weeks ( $\pm 1$  week)
- Concomitant medications review, limited to subsequent anti-cancer therapy

- Adverse event assessment (only if deemed related to PTX-35)

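### The only efficacy set requires an on-treatment scan, so treated patients who die, fail or stop before one drop out of any response summary made in it

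*Combined protocol and SAP*

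**What the plan says.** Section 9.1 defines three analysis sets: safety, DLT and efficacy evaluable. The efficacy set takes patients with RECIST-measurable disease before treatment "who received at least 1 dose of PTX-35 and who had at least one radiological assessment during treatment". The statistical methods part of the synopsis repeats the condition ("who had at least one radiological assessment during treatment"). Neither place makes an exception for early death, clinical progression or stopping for toxicity.

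Other provisions bear on who meets the condition:

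- **Scan timing.** Section 6.1.2 schedules response assessment "with planned evaluation performed every 8 weeks", with a one-week window either side, counted from C1D1. Footnote f of Table 2 and section 9.4 agree.
- **Stopping.** Section 5.4 says "Protocol therapy will be discontinued at any time if any of the following situations occur", and its list includes death, adverse event and withdrawal by the patient.
- **Prognosis at entry.** Section 5.1 asks only that patients "Have life expectancy of at least three months".
- **Replacement.** Under 5.4.2, "Patients who discontinue due to toxicity (related to PTX-35) during the 4-week DLT window of observation" are not replaced. Those who stop in Cycles 1–2 for other reasons are.
- **Scans after stopping.** Section 7.5 sends patients who stop without progression to Post-Treatment Follow-Up: "The following assessments will be performed every 8 weeks from the date of last scan".

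For reporting, the synopsis says "Categorical variables will be presented with numbers and, if meaningful, percentages". Section 9.0 calls for incidence and percent by dose cohort, and for listings of all patient data. Section 9.4 says BOR, PFS and OS are derived patient by patient and names no analysis set.

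**The concern.** Membership of the efficacy set depends on something that happens after treatment starts and that early failure can prevent. Patients who do badly early are less likely to be scanned on treatment, so the set selects patients who did well enough to reach a scan.

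The loss may also differ by dose. A patient who stops for toxicity in the DLT window counts in the DLT assessment. Unless there was an earlier unscheduled scan, the same patient is missing from the efficacy set, even if follow-up scans exist. If toxicity rises with dose, more patients would be removed at higher doses.

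Results are shown by dose cohort, and cohorts have 3 to 6 patients, so one missing patient changes the denominator visibly. Section 9.8 leaves open a later amendment to expand cohorts in light of response by dose level or tumor type. It sets no response threshold and names no analysis set. That is the one place where the denominator could influence a decision.

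**Working it through.** The plan states no response rate, early-loss rate or efficacy sample size, so it has no figure to reproduce. The check covers timing, denominators and a probability under assumed rates.

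**1. Timing.** Cycles last 14 days (section 4.2), so doses fall on days 1, 15, 29, 43 and 57 if nothing is delayed. Week 8 from C1D1 is day 57, and ± 7 days gives days 50–64. Four or five doses come before the first planned scan. The 4-week DLT window closes about a month earlier.

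**2. One route through the text.** A patient with measurable disease stops for toxicity in Cycle 1 or 2.
- 5.4.2: the patient is not replaced and counts for DLT.
- 7.5: without progression, the patient enters Post-Treatment Follow-Up and is scanned there.
- 9.1: those scans are after treatment, so without an earlier unscheduled scan the patient is outside the efficacy set.

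**3. Denominator effect.** Let N be the treated patients with measurable disease in a cohort, d those without an on-treatment scan, and x the responders among the scanned. The proportion goes from x/N to x/(N−d), a factor of N/(N−d).

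| N | d | x | All treated | Efficacy set | Factor |
|---|---|---|---|---|---|
| 3 | 1 | 1 | 1/3 = 33.3% | 1/2 = 50.0% | 3/2 = 1.50 |
| 6 | 1 | 1 | 1/6 = 16.7% | 1/5 = 20.0% | 6/5 = 1.20 |
| 6 | 2 | 1 | 1/6 = 16.7% | 1/4 = 25.0% | 6/4 = 1.50 |

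With x = 0 both proportions are 0%. The shift can also go the other way: if the excluded patient's response is seen only off treatment, 1/3 is shown as 0/2. Appendix II ends the BOR window at the end of treatment, so it would not count that response either.

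**4. How often a cohort's proportion would be raised.** This needs at least one scanned responder and at least one unscanned patient in the same cohort. Let u be the chance of being unscanned and r the chance of being scanned and a responder, with patients independent and all having measurable disease. Then

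P = 1 − (1−r)^n − (1−u)^n + (1−u−r)^n.

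Example with n = 3, u = 0.2, r = 0.10: 1 − 0.729 − 0.512 + 0.343 = 0.102.

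| u (assumed) | n=3, r=0.05 | n=3, r=0.10 | n=6, r=0.05 | n=6, r=0.10 |
|---|---|---|---|---|
| 0.1 | 2.8% | 5.4% | 11.1% | 19.9% |
| 0.2 | 5.2% | 10.2% | 18.1% | 32.4% |
| 0.3 | 7.4% | 14.4% | 22.3% | 39.8% |

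**The case against.** The strongest reply is that the plan never says BOR will be summarised in this set. Section 9.4 speaks of each patient and names no population, so the loss follows only if the set is used for response. That stands, and the point is worded accordingly. But the plan gives the set no other stated purpose, so 9.4 needs a sentence in either case.

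The stakes are also limited. Efficacy is exploratory, to be evaluated only where possible, and descriptive. Listings will show every patient. Escalation rests on DLTs and the Treg plateau, and expansion would need a protocol amendment. All of this stands and limits the consequence. It does not settle the denominator of the summary that readers will see.

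The probabilities rest on assumed rates. Three patients is the default cohort size, so the n = 3 columns are the more typical ones and 39.8% is an extreme corner. Measurable disease is not an entry requirement, so actual denominators may be smaller than the cohort. Not every patient with a DLT stops, since section 6.3 allows continuation at a reduced dose with approval. An unscheduled on-treatment scan also keeps a patient in the set. These points affect how often patients are lost, not whether the definition excludes them.

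Finally, the remedy does not recover a response seen only off treatment: 0/2 becomes 0/3, not 1/3. That is correct, because the Appendix II window is left alone.

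**Conclusion.** The concern holds. As defined, the only efficacy set is conditioned on a post-baseline event and excludes treated patients with measurable disease who have no scan on treatment. A response summary made in it overstates the all-treated proportion by N/(N−d) whenever a scanned patient has responded: by a factor of 1.2 to 1.5 for one or two losses in the cohorts worked above. The chance of this happening in a given cohort depends on rates the documents do not give. It is 2.8–14.4% for three patients and 11.1–39.8% for six, under 10–30% unscanned and 5–10% scanned responders.

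The conclusion assumes that the set is used for response, which the plan implies but does not state. It does not extend to PFS or OS, which the plan does not restrict to this set, nor to dose escalation or safety. The change should be made because it costs little and removes an avoidable selection from the response figure that 9.8 may draw on.

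**What to change.** Amend 9.1, 9.4 and the synopsis as follows:

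- Summarise BOR in all treated patients with measurable disease at baseline, including those later replaced.
- Count patients with no post-baseline scan in the existing Appendix II window (start to end of treatment) as NE, and keep them in the denominator as non-responders. Appendix II already has an NE category but applies it to pairs of time points, so the rule for a patient who is never scanned must be written out.
- Report the number of such patients and the reasons, by dose level.
- Keep the current scanned subset as a labelled sensitivity analysis.
- As a clarification only, state that PFS and OS use all treated patients from C1D1, with death before the first scan counted as a PFS event.

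The Appendix II BOR window does not change. The cost is wording, with no new data or visits. The reported response proportion may be slightly less favourable.

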## 9.2 Endpoints

### 9.2.1 Primary

- Number of Dose-limiting toxicities (DLTs) per NCI CTCAE v5.0.
- Frequency of treatment-emergent adverse events (TEAEs) and serious adverse events (SAEs) related to PTX-35 during the trial.

### 9.2.2 Secondary

- Optimal Immunological Dose (OID; dose where T-reg plateau is observed) or Maximum tolerated dose (MTD; highest dose level at which  $\leq 1$  patient of at least 6 patients experienced a DLT during the first two treatment cycles).
- Pharmacokinetic parameters will include maximum concentration ( $C_{max}$ ), area under curve up to the last measurable concentration ( $AUC_{last}$ ), trough observed serum concentration ( $C_{trough}$ ) and terminal elimination half-life ( $T_{1/2\lambda_z}$ ).

### **9.2.3 Exploratory**

Immune phenotype profiling of immune cell subsets will be conducted by flow cytometry in peripheral blood at various time-points to assess change from baseline in:

- Percentage of Treg cells (immunological effect)
- Frequency of anti-therapeutic antibody (ATA) titers to PTX-35 (Immunogenicity)
- General immunologic expansion: The frequency and expansion of NK, CD4 and CD8 T cell subsets
- Specific antigen driven immune expansion: immune responses to a well-characterized first-time exposure or recall antigen based on the patient's HLA type will be measured at baseline and on study using ELISA, ELISPOT and flow cytometric methods.
- Specific cytokine expression in response to treatment with PTX-35.

Clinical benefit will be evaluated where possible for:

- Best Overall Response, Overall Survival and Progression-Free Survival assessed by RECIST 1.1.

### **9.3 Safety**

Safety will be assessed throughout the study by means of physical examination, weight, vital signs, ECOG performance status, laboratory evaluations (hematology, biochemistry and cytokines), electrocardiogram (ECG), and recording of concurrent illness/therapy and treatment-emergent adverse events. CTCAE version 5.0 will be used to grade all toxicities. All related adverse events will be monitored until resolution or permanent outcome. Concomitant medications will be recorded throughout the study.

Cytokines will be monitored during cycle 1 and 2. Patients will also be monitored for any clinical symptoms associated with elevated cytokine levels. Cytokines will only be monitored at cycle 3 and beyond if patient is symptomatic (i.e., flu-like symptoms, fever, or allergic reactions).

Safety data will be summarized for the safety evaluable population. These data will include Treatment emergent adverse events (TEAEs) and laboratory parameters. Adverse event terms will be coded using the most current version of Medical Dictionary for Drug Regulatory Activities (MedDRA).

### **9.4 Efficacy**

Assessment of tumor response will be performed every 8 weeks ( $\pm$  1 week) from C1D1 until disease progression according to RECIST 1.1 ([APPENDIX II](#)). Best overall response (BOR), Overall Survival (OS) and Progression-Free Survival (PFS) will be determined for each patient.

